10.3.4. Reporting of SAEs

SAE Reporting to Pfizer Safety via CT SAE Report Form

- Facsimile transmission of the CT SAE Report Form is the preferred method to transmit this information to Pfizer Safety.
- In circumstances when the facsimile is not working, notification by telephone is acceptable with a copy of the CT SAE Report Form sent by overnight mail or courier service.
- Initial notification via telephone does not replace the need for the investigator to complete and sign the CT SAE Report Form pages within the designated reporting time frames.

10.4. Appendix 4: Contraceptive and Barrier Guidance

10.4.1. Male Participant Reproductive Inclusion Criteria

Male participants are eligible to participate if they agree to the following requirements during the intervention period and for at least 28 days after the last dose of study intervention, which corresponds to the time needed to eliminate reproductive safety risk of the study intervention(s):

- Refrain from donating sperm.

PLUS either:

- Be abstinent from heterosexual intercourse with a female of childbearing potential as their preferred and usual lifestyle (abstinent on a long-term and persistent basis) and agree to remain abstinent.

OR

- Must agree to use contraception/barrier as detailed below:
 - Agree to use a male condom and should also be advised of the benefit for a female partner to use a highly effective method of contraception as a condom may break or leak when having sexual intercourse with a woman of childbearing potential who is not currently pregnant.
 - In addition to male condom use, a highly effective method of contraception may be considered in WOCBP partners of male participants (refer to the list of highly effective methods below in [Section 10.4.4](#)).

10.4.2. Female Participant Reproductive Inclusion Criteria

A female participant is eligible to participate if she is not pregnant or breastfeeding, and at least 1 of the following conditions applies:

- Is not a WOCBP (see definitions below in [Section 10.4.3](#)).

OR

- Is a WOCBP and using a contraceptive method that is highly effective (with a failure rate of <1% per year), with low user dependency, as described below during the intervention period and for at least 28 days after the last dose of study intervention, which corresponds to the time needed to eliminate any reproductive safety risk of the study intervention(s). The investigator should evaluate the effectiveness of the contraceptive method in relationship to the first dose of study intervention.

A WOCBP agrees not to donate eggs (ova, oocytes) for the purpose of reproduction during this period. The investigator should evaluate the effectiveness of the contraceptive method in relationship to the first dose of study intervention.

The investigator is responsible for review of medical history, menstrual history, and recent sexual activity to decrease the risk for inclusion of a woman with an early undetected pregnancy.

10.4.3. Woman of Childbearing Potential

A woman is considered fertile following menarche and until becoming postmenopausal unless permanently sterile (see below).

If fertility is unclear (eg, amenorrhea in adolescents or athletes) and a menstrual cycle cannot be confirmed before the first dose of study intervention, additional evaluation should be considered.

Women in the following categories are not considered WOCBP:

1. Premenopausal female with 1 of the following.

- Documented hysterectomy;
- Documented bilateral salpingectomy;
- Documented bilateral oophorectomy.

For individuals with permanent infertility due to an alternate medical cause other than the above, (eg, mullerian agenesis, androgen insensitivity), investigator discretion should be applied to determining study entry.

Note: Documentation for any of the above categories can come from the site personnel's review of the participant's medical records, medical examination, or medical history interview. The method of documentation should be recorded in the participant's medical record for the study.

2. Postmenopausal female.

- A postmenopausal state is defined as no menses for 12 months without an alternative medical cause. In addition:
 - A high FSH level in the postmenopausal range must be used to confirm a postmenopausal state in women under 60 years old and not using hormonal contraception or HRT.
 - A female on HRT and whose menopausal status is in doubt will be required to use one of the nonestrogen hormonal highly effective contraception methods

if they wish to continue their HRT during the study. Otherwise, they must discontinue HRT to allow confirmation of postmenopausal status before study enrollment.

10.4.4. Contraception Methods

Contraceptive use by men or women should be consistent with local availability/regulations regarding the use of contraceptive methods for those participating in clinical trials.

Highly Effective Methods That Have Low User Dependency

1. Implantable progestogen-only hormone contraception associated with inhibition of ovulation.
2. Intrauterine device.
3. Intrauterine hormone-releasing system.
4. Bilateral tubal occlusion (eg, bilateral tubal ligation).
5. Vasectomized partner.
 - A vasectomized partner is a highly effective contraceptive method provided that the partner is the sole sexual partner of the WOCBP and the absence of sperm has been confirmed. If not, an additional highly effective method of contraception should be used. The spermatogenesis cycle is approximately 90 days.
6. Sexual abstinence.
 - Sexual abstinence is considered a highly effective method only if defined as refraining from heterosexual intercourse during the entire period of risk associated with the study intervention. The reliability of sexual abstinence needs to be evaluated in relation to the duration of the study and the preferred and usual lifestyle of the participant.

10.5. Appendix 5: Liver Safety: Suggested Actions and Follow-Up Assessments

Potential Cases of Drug-Induced Liver Injury

Humans exposed to a drug who show no sign of liver injury (as determined by elevations in transaminases) are termed “tolerators,” while those who show transient liver injury but adapt are termed “adaptors.” In some participants, transaminase elevations are a harbinger of a more serious potential outcome. These participants fail to adapt and therefore are “susceptible” to progressive and serious liver injury, commonly referred to as DILI. Participants who experience a transaminase elevation above $3 \times$ ULN should be monitored more frequently to determine if they are “adaptors” or are “susceptible.”

In the majority of DILI cases, elevations in AST and/or ALT precede Tbili elevations ($>2 \times$ ULN) by several days or weeks. The increase in Tbili typically occurs while AST/ALT is/are still elevated above $3 \times$ ULN (ie, AST/ALT and Tbili values will be elevated within the same laboratory sample). In rare instances, by the time Tbili elevations are detected, AST/ALT values might have decreased. This occurrence is still regarded as a potential DILI. Therefore, abnormal elevations in either AST OR ALT in addition to Tbili that meet the criteria outlined below are considered potential DILI (assessed per Hy’s law criteria) cases and should always be considered important medical events, even before all other possible causes of liver injury have been excluded.

The threshold of laboratory abnormalities for a potential DILI case depends on the participant’s individual baseline values and underlying conditions. Participants who present with the following laboratory abnormalities should be evaluated further as potential DILI (Hy’s law) cases to definitively determine the etiology of the abnormal laboratory values:

- Participants with AST/ALT and Tbili baseline values within the normal range who subsequently present with AST OR ALT values $>3 \times$ ULN AND a Tbili value $>2 \times$ ULN with no evidence of hemolysis and an alkaline phosphatase value $<2 \times$ ULN or not available.
- For participants with baseline AST **OR** ALT **OR** Tbili values above the ULN, the following threshold values are used in the definition mentioned above, as needed, depending on which values are above the ULN at baseline:
 - Preexisting AST or ALT baseline values above the normal range: AST or ALT values >2 times the baseline values AND $>3 \times$ ULN; or $>8 \times$ ULN (whichever is smaller).
 - Preexisting values of Tbili above the normal range: Tbili level increased from baseline value by an amount of at least $1 \times$ ULN **or** if the value reaches $>3 \times$ ULN (whichever is smaller).

Rises in AST/ALT and Tbili separated by more than a few weeks should be assessed individually based on clinical judgment; any case where uncertainty remains as to whether it represents a potential Hy's law case should be reviewed with the sponsor.

The participant should return to the investigator site and be evaluated as soon as possible, preferably within 48 hours from awareness of the abnormal results. This evaluation should include laboratory tests, detailed history, and physical assessment.

In addition to repeating measurements of AST and ALT and Tbili for suspected Hy's law cases, additional laboratory tests should include albumin, CK, direct and indirect bilirubin, GGT, PT/INR, total bile acids, and alkaline phosphatase. Consideration should also be given to drawing a separate tube of clotted blood and an anticoagulated tube of blood for further testing, as needed, for further contemporaneous analyses at the time of the recognized initial abnormalities to determine etiology. A detailed history, including relevant information, such as review of ethanol, acetaminophen/paracetamol (either by itself or as a coformulated product in prescription or over-the-counter medications), recreational drug, or supplement (herbal) use and consumption, family history, sexual history, travel history, history of contact with a jaundiced person, surgery, blood transfusion, history of liver or allergic disease, and potential occupational exposure to chemicals, should be collected. Further testing for acute hepatitis A, B, C, D, and E infection, liver imaging (eg, biliary tract), and collection of serum samples for acetaminophen/paracetamol drug and/or protein adduct levels may be warranted.

All cases demonstrated on repeat testing as meeting the laboratory criteria of AST/ALT and Tbili elevation defined above should be considered potential DILI (Hy's law) cases if no other reason for the LFT abnormalities has yet been found. **Such potential DILI (Hy's law) cases are to be reported as SAEs, irrespective of availability of all the results of the investigations performed to determine etiology of the LFT abnormalities.**

A potential DILI (Hy's law) case becomes a confirmed case only after all results of reasonable investigations have been received and have excluded an alternative etiology.

10.6. Appendix 6: ECG Findings of Potential Clinical Concern

ECG Findings That May Qualify as AEs

Marked sinus bradycardia (rate <40 bpm) lasting minutes.New PR interval prolongation >280 msec.New prolongation of QTcF to >480 msec (absolute) or by \geq60 msec from baseline.New-onset atrial flutter or fibrillation, with controlled ventricular response rate: ie, rate <120 bpm.New-onset type I second-degree (Wenckebach) AV block of >30 seconds' duration.Frequent PVCs, triplets, or short intervals (<30 seconds) of consecutive ventricular complexes.
ECG Findings That May Qualify as SAEs

QTcF prolongation >500 msec.New ST-T changes suggestive of myocardial ischemia.New-onset left bundle branch block (QRS >120 msec).New-onset right bundle branch block (QRS >120 msec).Symptomatic bradycardia.Asystole:
In awake, symptom-free participants in sinus rhythm, with documented periods of asystole \geq3.0 seconds or any escape rate <40 bpm, or with an escape rhythm that is below the AV node.In awake, symptom-free participants with atrial fibrillation and bradycardia with 1 or more pauses of at least 5 seconds or longer.Atrial flutter or fibrillation, with rapid ventricular response rate: rapid = rate >120 bpm.Sustained supraventricular tachycardia (rate >120 bpm) ("sustained" = short duration with relevant symptoms or lasting >1 minute).

- Ventricular rhythms >30 seconds' duration, including idioventricular rhythm (heart rate <40 bpm), accelerated idioventricular rhythm (HR >40 bpm to <100 bpm), and monomorphic/polymorphic ventricular tachycardia (HR >100 bpm (such as torsades de pointes)).
- Type II second-degree (Mobitz II) AV block.
- Complete (third-degree) heart block.

ECG Findings That Qualify as SAEs

- Change in pattern suggestive of new myocardial infarction.
- Sustained ventricular tachyarrhythmias (>30 seconds' duration).
- Second- or third-degree AV block requiring pacemaker placement.
- Asystolic pauses requiring pacemaker placement.
- Atrial flutter or fibrillation with rapid ventricular response requiring cardioversion.
- Ventricular fibrillation/flutter.
- At the discretion of the investigator, any arrhythmia classified as an adverse experience.

The enumerated list of major events of potential clinical concern are recommended as “alerts” or notifications from the core ECG laboratory to the investigator and Pfizer study team, and not to be considered as all inclusive of what to be reported as AEs/SAEs.

10.7. Appendix 7: Abbreviations

The following is a list of abbreviations that are used in the protocol.

Abbreviation	Term
3CL ^{pro}	3C-like protease
Abs	absolute
ADL	activities of daily living
AE	adverse event
AESI	adverse events of special interest
CCI	[REDACTED]
CCI	[REDACTED]
ALT	alanine aminotransferase
aPTT	activated partial thromboplastin time
AST	aspartate aminotransferase
ATG	antithyroglobulin antibody
aTPO	anti-thyroid peroxidase
AUC	area under the curve
AUC ₁₂	area under the plasma concentration-time profile from time 0 to time point on 12 hours
AUC _{last}	area under the plasma concentration-time profile from time 0 to the time of the last quantifiable concentration (C _{last})
AUC _{tau}	area under the plasma concentration-time profile from time 0 to the time of the end of the dosing interval (tau), where tau=12 hours
AV	atrioventricular
b-hCG	beta-human chorionic gonadotropin
BID	twice daily
BMI	body mass index
BP	blood pressure
bpm	beats per minute
BUN	blood urea nitrogen
C _{av}	average concentration
CDK-EPI	Chronic Kidney Disease-Epidemiology Collaboration
CFR	Code of Federal Regulations
CL/F	apparent clearance
CCI	[REDACTED]
CIOMS	Council for International Organizations of Medical Sciences
CK	creatine kinase
C _{max}	maximum observed concentration
CO ₂	carbon dioxide (bicarbonate)
COVID-19	coronavirus disease 2019

Abbreviation	Term
CRF	case report form
CRO	contract research organization
CRU	clinical research unit
CSR	clinical study report
CT	clinical trial; computerized tomography
C_{trough}	trough concentration
CYP	cytochrome P450
CYP3A	cytochrome P450 3A
CYP3A4	cytochrome P450 3A4
CYP3A5	cytochrome P450 3A5
DILI	drug-induced liver injury
DMC	data monitoring committee
dNHBE	differentiated normal human bronchial epithelial
EC	ethics committee
EC ₉₀	concentration required for 90% effect
ECC	emergency contact card
ECG	electrocardiogram
eCRF	electronic case report form
EDB	exposure during breastfeeding
EDP	exposure during pregnancy
eGFR	estimated glomerular filtration rate
EMA	European Medicines Agency
EU	European Union
EudraCT	European Clinical Trials Database
FIH	first-in-human
f_m	fraction metabolized
FSH	follicle-stimulating hormone
GCP	Good Clinical Practice
GGT	gamma-glutamyl transferase
GLP	Good Laboratory Practice
HBcAb	hepatitis B core antibody
HBsAg	hepatitis B surface antigen
HCoV-229E	human coronavirus 229E
HCoV-HKU1	human coronavirus HKU1
HCoV-NL63	human coronavirus NL63
HCoV-OC43	human coronavirus OC43
HCV	hepatitis C virus
HCVAb	hepatitis C antibody
HIV	human immunodeficiency virus
HR	heart rate
HRT	hormone replacement therapy

Abbreviation	Term
IB	investigator's brochure
ICD	informed consent document
ICH	International Council for Harmonisation
ID	identification
IND	investigational new drug
INR	international normalized ratio
IP manual	investigational product manual
IPAL	Investigational Product Accountability Log
IRB	institutional review board
IQMP	integrated quality management plan
IV	intravenous
K _i	inhibition constant
LBBB	left bundle branch block
LFT	liver function test
M&E	metabolism and excretion
MAD	multiple ascending dose
MCH	mean corpuscular hemoglobin
MCHC	mean corpuscular hemoglobin concentration
MCV	mean corpuscular volume
MERS	Middle East respiratory syndrome
msec	millisecond
N/A	not applicable
NHP	non-human primate
NOAEL	no-observed-adverse-effect level
NSAE	non-serious adverse event
NYHA	New York Heart Association functional classification
PCR	polymerase chain reaction
PD	pharmacodynamic(s)
PE	physical examination
PK	pharmacokinetic(s)
PR	pulse rate
PT	prothrombin time
PT/INR	prothrombin time/international normalized ratio
PTR	peak-to-trough ratio
PVC	premature ventricular contraction/complex
q12h	every 12 hours
QTc	corrected QT
QTcF	corrected QT (Fridericia method)
QTL	quality tolerance limit
qual	qualitative
R _{ac}	accumulation ratio for AUC _{tau} following multiple dosing

Abbreviation	Term
$R_{ac\ C_{max}}$	accumulation ratio for C_{max}
RBC	red blood cell
RNA	ribonucleic acid
RR	respiratory rate
SAD	single ascending dose
SAE	serious adverse event
SAP	statistical analysis plan
SARS-CoV-1	severe acute respiratory syndrome coronavirus 1
SARS-CoV-2	severe acute respiratory syndrome coronavirus 2
SCr	serum creatinine
SE	Supratherapeutic Exposure
SoA	schedule of activities
SOP	standard operating procedure
SRSD	single reference safety document
SUSAR	suspected unexpected serious adverse reaction
$t_{1/2}$	terminal elimination half-life
T4	Thyroxine
TBili	total bilirubin
TEAE	treatment-emergent adverse event
THC	tetrahydrocannabinol
T_{max}	time for C_{max}
TSH	thyroid stimulating hormone
ULN	upper limit of normal
US	United States
V_z/F	apparent volume of distribution
WBC	white blood cell
WHO	World Health Organization
WOCBP	woman/women of childbearing potential

1. VERSION HISTORY

Table 1. Summary of Changes

Version/ Date	Associated Protocol Amendment	Rationale	Specific Changes
1 16 Nov 2021	Original 27 Sep 2021	N/A	N/A

2. INTRODUCTION

The purpose of the study is to investigate the PK, safety and tolerability of PF-07321332 following repeated oral doses in combination with a PK boosting agent ritonavir in Chinese healthy adults. One (or more) suitable Western study(ies) will be selected for comparison between Western and Chinese population. This may involve comparison of Day 1 data and/or steady state data (generally reached by Day 2) with the data obtained from the Chinese Phase 1 study. The comparison results will be used to bridge global clinical data and support China registration of PF-07321332.

This statistical analysis plan (SAP) provides the detailed methodology for summary and statistical analyses of the data collected in Study C4671016. This document may modify the plans outlined in the protocol; however, any major modifications of the primary endpoint definition or its analysis will also be reflected in a protocol amendment.

2.1. Study Objectives, Endpoints, and Estimands

There are no estimands for this study.

Objectives	Endpoints
Primary:	Primary:

 • To characterize the plasma PK of PF-07321332 when PF-07321332/ritonavir is administered in healthy Chinese participants 	
 • PF-07321332 plasma PK parameters: 
 • Day 1: C_{max}, T_{max}, AUC_{12} • Day 5, 8, 10 (pre-dose and 12 hours after last dose): C_{trough} • Day 10: C_{max}, T_{max}, AUC_{tau}; and if data permit, AUC_{last}, C_{av}, R_{ac}, $R_{ac,Cmax}$, PTR, CL/F, V_z/F and $t_{1/2}$
Secondary:	Secondary:

 • To determine the safety and tolerability of PF-07321332/ritonavir in healthy Chinese participants after dose administration • To characterize the plasma PK of ritonavir following PF-07321332/ritonavir administration in healthy Chinese participants 	
 • AEs, clinical safety laboratory tests, vital signs, 12-lead ECGs • Ritonavir plasma PK parameters: 
 • Day 1: C_{max}, T_{max}, AUC_{12} • Day 5, 8, 10 (pre-dose and 12 hours after last dose): C_{trough} • Day 10: C_{max}, T_{max}, AUC_{tau}; and if data permit, AUC_{last}, C_{av}, CL/F, V_z/F and $t_{1/2}$
CCI	

2.2. Study Design

This is a Phase 1, open-label study to estimate the PK, safety and tolerability of PF-07321332 when PF-07321332/ritonavir is administered in healthy Chinese participants. The study will consist of 1 treatment: 10-day oral doses of 300 mg PF 07321332/100 mg ritonavir. A total of approximately 14 healthy male and/or female participants will be enrolled into the study to ensure at least 12 participants will complete the study. Participants who discontinue from the study for non-safety reasons may be replaced at the sponsor's discretion in collaboration with the Investigator.

The total duration of participation in this study is approximately 73 days, including a screening period of up to 28 days to confirm eligibility, treatment duration about 12 days (10 days of dose duration and another 2 days of full PK profile duration) and a follow-up period of approximately 28-35 days post the last dose of study intervention.

All of participants will receive PF-07321332 and ritonavir together. The dose regimen is PF-07321332/ritonavir 300/100 mg q12h for a total of 19 oral doses (Day 1 to Day 10). The first dose and the last dose will be recommended to be administrated on Day 1 and Day 10 morning, respectively, for intensive PK sample collection feasibility. The evening dose will not be given on Day 10.

3. ENDPOINTS AND BASELINE VARIABLES: DEFINITIONS AND CONVENTIONS

As listed in [Section 2.1](#) the primary endpoints (PF-07321332 plasma PK) as well as the secondary (ritonavir plasma PK) **CCI** [REDACTED] are related to PK and are described herein.

Samples for the PK analysis of PF-07321332 and ritonavir will be taken according to the schedule of activities (SoA) given in the protocol.

The PK parameters of PF-07321332 and ritonavir will be derived (if data permit) from the concentration-time data using standard non-compartmental methods. Plasma **CCI** [REDACTED] PK parameters are described in Table 2. Actual PK sampling times will be used in the derivation of PK parameters. In the case that actual PK sampling times are not available, nominal PK sampling time will be used in the derivation of PK parameters.

Table 2. Plasma **CCI [REDACTED] PK Parameters**

Parameter	Analyte	Day(s)	Definition	Method of Determination
AUC_{last}^a	PF-07321332/ ritonavir	10	Area under the plasma concentration-time profile from time 0 to the time of the last quantifiable concentration (C_{last})	Linear/Log trapezoidal method.
AUC_{12}	PF-07321332/ ritonavir	1	Area under the plasma concentration-time profile from time 0 to time point on 12 hours, on Day 1	Linear/Log trapezoidal method.
AUC_{tau}	PF-07321332/ ritonavir	10	Area under the plasma concentration-time profile from time 0 to the time of the end of the dosing interval (tau), where $tau=12$ hours	Linear/Log trapezoidal method.
C_{max}	PF-07321332/ ritonavir	1, 10	Maximum plasma concentration during the dosing interval	Observed directly from data.
T_{max}	PF-07321332/ ritonavir	1,10	Time for C_{max}	Observed directly from data as time of first occurrence.
$T_{1/2}^a$	PF-07321332/ ritonavir	10	Terminal elimination half-life	Log_e(2)/k_{el}, where k_{el} is the terminal phase rate constant calculated by a linear regression of the log-linear concentration-time curve. Only those data points judged to describe the terminal log-linear decline will be used in the regression.
CL/F^a	PF-07321332/ ritonavir	10	Apparent clearance	Dose/AUC_{tau}.
V_z/F^a	PF-07321332/ ritonavir	10	Apparent volume of distribution	Dose/($AUC_{tau} \times k_{el}$).

Table 2. Plasma CCI PK Parameters

Parameter	Analyte	Day(s)	Definition	Method of Determination
C_{trough}	PF-07321332/ ritonavir	5, 8, 10	Pre-dose concentration	Observed directly from data, pre-dose and 12 hours after last dose for Day 10.
C_{av}^a	PF-07321332/ ritonavir	10	Average concentration	$AUC_{tau}(\text{Day 10})/12 \text{ hours}$.
R_{ac}^a	PF-07321332	10	Accumulation ratio for AUC_{tau} following multiple dosing	$AUC_{tau}(\text{Day 10})/AUC_{12}(\text{Day 1})$.
$R_{ac,Cmax}^*$	PF-07321332	10	Accumulation ratio for C_{max}	$C_{max}(\text{Day 10})/C_{max}(\text{Day 1})$.
PTR^*	PF-07321332	10	Peak-to-trough ratio	$C_{max}(\text{Day 10})/C_{trough}(\text{Day 10})$. at steady state.
CCI				
CCI				
CCI				

a. As data permit.

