- a. PK blood sample should be collected within 10 min before the study intervention administration in the evening on Day 1.
- b. PK blood sample should be collected within 30 min before the study intervention administration in the morning on Day 1, Day 5 and Day 8.
- c. [REDACTED]
- d. On Day 1, vital signs and 12-lead ECGs (triplicate) are to be collected pre-dose (within 2 hours before administration), and within 1 hour to 2 hours after administration in the morning.

Visit Identifier	Schedules for Days 10-12										
Study Day	10									11-12	
Hours Post Dose on Study Day 10	0	0.5	1	1.5	2	4	6	8	12	24	48
Study intervention administration ^a	X										
PK blood sampling	X ^b	X	X	X	X	X	X	X	X	X	X
CCI	█	█	█	█	█	█	█	█	█		
12-Lead ECG (triplicate) ^d	X		→	→	→						
Vital signs (BP/PR/RR/temperature) ^d	X		→	→	→						

- a. The last dose will be administrated in the morning on Day 10, since no evening dose will be given on Day 10.
- b. PK blood sample should be collected within 30 min before the study intervention administration in the morning.
- c. [REDACTED]
- d. On Day 10, vital signs and 12-lead ECGs (triplicate) are to be collected pre-dose (within 2 hours before administration), and within 1 hour to 2 hours after administration in the morning.

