9.3.1. Statistical Methods for Pharmacokinetic data

The PK parameters of PF-07321332 and ritonavir will be listed and descriptively summarized by study day, respectively. For AUCs and C_{max} , box whisker plots for individual participant parameters overlaid with geometric means will be plotted for each analyte. For pre-dose concentration, plot of C_{trough} over time will be provided for each analyte. The PK parameters of PF-07321332 and ritonavir obtained in this study will be compared to the corresponding PK data from one or more global completed/ongoing studies which will be defined in SAP. The detailed statistical analysis will also be described in SAP. The comparative PK data for PF-07321332 and ritonavir may be from different studies depends on the specific study design. These results may be reported separately from the clinical study report (eg, ethnic sensitivity analysis report, brief document for submission, or other appropriate documents).

The concentrations of PF-07321332 and ritonavir will be listed and descriptively summarized by study day and nominal PK sampling times. For each analyte, individual participant and summary profiles (mean and median plots) of the plasma concentration time data will be plotted using actual and nominal sampling times, respectively. Additional specifications about the tables, listings, and figures will be outlined in the SAP.

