6. ANALYSES AND SUMMARIES

6.1. Primary Endpoint(s)

The PK parameters detailed in [Section 3.1](#) will be listed and descriptively summarized for participants in the PK parameter analysis set (as defined in [Section 4](#)). Missing values will be handled as detailed in [Section 5.3.2](#). For each analyte (PF-07321332 plasma, **CC1** [REDACTED] and ritonavir plasma), the PK parameters will be summarized by study day. Each summary will include the set of summary statistics as specified in [Table 3](#).

Table 3. PK Parameters to be Summarized Descriptively

Parameter	Summary Statistics
C_{max} , AUC_{12} , C_{trough} , AUC_{tau} , AUC_{last} , C_{av} , R_{ac} , $R_{ac,Cmax}$, PTR, CL/F, V_z/F , CCI	N, arithmetic mean, median, cv%, SD, minimum, maximum, geometric mean and geometric cv%.
T_{max}	N, median, minimum, maximum.
$t_{1/2}$	N, arithmetic mean, median, SD, minimum, maximum.

For AUCs and C_{max} , box and whisker plots for individual participant parameters overlaid with geometric means will be plotted for each analyte. For C_{max} , box and whisker plots will be presented with both Days 1 and 10 on the same figure by analyte. C_{trough} over time will be plotted for each analyte. Supporting data from the estimation of $t_{1/2}$ will be listed by analyte where applicable.

For each analyte, the PK concentrations will be presented using participants in the PK concentration analysis set (as defined in [Section 4](#)) and will include:

- a listing of all concentrations sorted by participant ID and nominal time post-dose. The concentration listing will also include the actual times. Deviations from the nominal time will be given in a separate listing.
- a summary of concentrations and nominal time post-dose, where the set of statistics will include n, mean, median, SD, cv%, minimum, maximum and the number of concentrations above the LLQ.
- median concentration-time plots (on both linear and semi-log scales) against nominal time post-dose.
- mean concentration-time plots (on both linear and semi-log scales) against nominal time post-dose.
- individual concentration-time plots by dose (on both linear and semi-log scales) against actual time post-dose.

All figures (individual, mean, and median) will be presented with both Days 1 and 10 on the same figures. The scale used for the x-axis (time) of these plots will be decided on review of the data, and will depend on how long PF-07321332 and ritonavir concentrations are quantifiable.

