The PK parameters of PF-07321332 and ritonavir on Day 1 and steady state obtained from this study will be used to compare with the corresponding PK parameters obtained from Studies C4671014 and C4671015 to evaluate the PK characteristics between Chinese and Western populations. These analyses and results will be presented separately from the clinical study report (eg, ethnic sensitivity analysis report or other appropriate documents).

PFIZER GENERAL BUSINESS

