7. INTERIM ANALYSES

7.1. Introduction

No formal interim analysis will be conducted for this study. As this is an open-label study, the sponsor may conduct unblinded reviews of the data during the course of the study for the purpose of safety assessment, facilitating PK/PD modeling, and/or supporting clinical development.

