Appendix 2. List of Abbreviations

Abbreviation	Term
CCI	[REDACTED]
Ae _{tau} %	percent of dose excreted in urine as unchanged drug
AUC	area under the concentration-time curve
AUC ₁₂	AUC from time 0 to 12 hours
AUC _{last}	AUC from time 0 to T _{last}
AUC _{tau}	AUC from time 0 to time tau
BLQ	below the limit of quantitation
BP	blood pressure
C _{av}	average concentration
C _{max}	maximum observed concentration
C _{trough}	pre-dose concentration
CCI	[REDACTED]
CL/F	apparent clearance
CV	coefficient of variation
ECG	electrocardiogram
ID	identification
LLQ	lower limit of quantitation
NC	not calculated
ND	not done
NS	not sample
N/A	not applicable
PD	pharmacodynamic(s)
PK	pharmacokinetic(s)
PTR	peak-to-trough ratio
QTc	corrected QT
QTcF	corrected QT (Fridericia method)
R _{ac}	accumulation ratio for AUC _{tau}
R _{ac,Cmax}	accumulation ratio for C _{max}
SAP	statistical analysis plan
SD	standard deviation
SoA	schedule of activities
T _{1/2}	terminal elimination half life
T4	thyroxine
T _{max}	time for C _{max}
TSH	thyroid stimulating hormone
TEAE	treatment-emergent adverse event
V _{z/F}	apparent volume of distribution

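### Does the peak-to-trough ratio need its Day 10 trough sample named in the SAP?

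*SAP*

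**What the plan says.** - **C_trough.** SAP Section 3, Table 2, defines it as "Pre-dose concentration" for Days 5, 8 and 10, and SAP Appendix 2 repeats "pre-dose concentration". The method column of the same row adds a second Day 10 time: "Observed directly from data, pre-dose and 12 hours after last dose for Day 10". The endpoint lists (Protocol Sections 1.1 and 3, SAP Section 2.1) also place both times under C_trough, and Protocol Table 1 matches SAP Table 2.
- **Dosing on Day 10.** Protocol Section 1.3 states: "The last dose will be administrated in the morning on Day 10, since no evening dose will be given on Day 10".
- **PTR.** Both tables give it as Day 10 C_max over Day 10 C_trough at steady state, for PF-07321332 only. No sample time is attached to the denominator. The endpoint lists include it under Primary, if data permit.
- **Presentation.** SAP Section 6.1 summarises PK parameters by study day and concentrations by nominal time, and lists every concentration with its actual time. On the trough plot, Protocol Section 9.3.1 begins "For pre-dose concentration, plot of" C_trough over time, while SAP Section 6.1 says that C_trough "over time will be plotted for each analyte".
- **Use.** SAP Section 5.1 plans no hypothesis test and no decision rule. SAP Section 6.1 says that Day 1 and steady-state parameters "will be used to compare with the corresponding PK parameters obtained from Studies C4671014 and C4671015", in a report separate from the clinical study report.

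**The concern.** A primary endpoint should give one value per participant, whoever programs it. Here two readings of one table give two. Under the definition column, the denominator is the 0 h sample on Day 10, which closes the interval after the Day 9 evening dose. Under the method column, it can also be the 12 h sample, which closes the interval that supplies Day 10 C_max and AUC_tau. The 12 h sample does not even meet the stated definition, because no dose comes after it. The by-day parameter table also has two Day 10 C_trough values and no stated way to show them.

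Three consequences seem possible. If PTR or C_trough enters the comparison with Studies C4671014 and C4671015, a different trough convention there would spoil the match. SAP Section 7.1 says that "the sponsor may conduct unblinded reviews of the data during the course of the study", so the denominator could in principle be picked after seeing data. And the trough plot might mix the two kinds of sample.

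**Working it through.** The plan gives no PTR value, trough CV or half-life, so it has no figure to reproduce. The check sets the texts side by side and then illustrates the size.

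**1. Does the 12 h sample precede a dose?** Doses: 9 days × 2 + 1 on Day 10 = 19, as stated. The Day 9 evening dose is dose 18 and the Day 10 morning dose is dose 19. The 0 h sample ends the interval after dose 18 and the 12 h sample ends the interval after dose 19. The definition column is therefore too narrow for the sample that the method column adds.

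**2. Are both valid steady-state troughs?** SAP Section 2 says that steady state is generally reached by Day 2. Both samples come on Day 10, at the end of a nominal 12 h interval. Either one fits a ratio described as at steady state.

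**3. Could the two values be merged unnoticed?** The endpoint lists name both times. Pooling them under one Day 10 heading would give N = 2 × 12 = 24 to 2 × 14 = 28 for 12 to 14 participants, which would show at once. The concentration summary by nominal time keeps 0 h and 12 h apart in any case.

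**4. Do the plot wordings conflict?** The SAP plots C_trough over time and defines C_trough as the pre-dose concentration. The protocol plots C_trough for pre-dose concentration. Under the SAP's own definition these agree. If the 12 h value is also plotted, it sits at its own place on the time axis.

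**5. How much could the choice move PTR?** C_max cancels, so PTR(12 h) / PTR(0 h) = C(0 h) / C(12 h).

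*Random variation.* Assumed: within-participant CV of 10%, 20% or 30%, independent errors, no systematic difference. Formulas: s = √ln(1 + CV²); SD of the log ratio = s√2; standard error for n = 12 is SD/√12; 95% range = exp(±1.96 × SE).

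| Assumed CV | s | SD of log ratio | Participants whose PTR moves by more than a factor of 1.2 | SE, n = 12 | 95% range, ratio of geometric means |
|---|---|---|---|---|---|
| 10% | 0.100 | 0.141 | 19.6% | 0.0407 | 0.92 to 1.08 |
| 20% | 0.198 | 0.280 | 51.5% | 0.0809 | 0.85 to 1.17 |
| 30% | 0.294 | 0.415 | 66.1% | 0.1198 | 0.79 to 1.26 |

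The fourth column is P(|log ratio| > ln 1.2). In every row the expected log ratio is 0, so neither denominator shifts the geometric mean in a known direction.

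*Sampling time.* Assumed: half-life of 4 to 12 h, k = ln 2 / half-life, factor = exp(k × difference in time since dose). Protocol Section 1.3 puts the pre-dose draw within 30 min before dosing. If it is 0.5 h early and the 12 h draw is on time, the factor is exp(0.5 × ln 2 / 4) = 1.09 at 4 h and exp(0.5 × ln 2 / 12) = 1.03 at 12 h. At the limits of the windows, the pre-dose draw falls 11.0 to 12.5 h after the previous dose (30 min dosing tolerance, Protocol Section 6.1.1) and the 12 h draw falls at 11 to 13 h (Protocol Section 8.4.1). The factor then runs from 0.77 to 1.41 at 4 h and from 0.92 to 1.12 at 12 h. These are worst cases for one participant.

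**The case for a change.** The best case for a change is that the ambiguity is real. Appealing to the definition column does not remove it, because the method column and the endpoint lists also call the 12 h sample C_trough. Listing both times does not say which one enters the ratio. Individual PTRs can differ noticeably, as the table shows, and a morning-to-evening difference, which the documents neither show nor exclude, would add to this: a 12 h value 20% below the pre-dose value raises PTR by 1/0.8 = 1.25. Naming the sample would need no new blood draw.

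The textual point stands. The consequences are weaker:

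- **Comparison.** The SAP does not say that PTR or C_trough is among the compared parameters, and these documents do not give the trough conventions of the two other studies. Fixing a denominator here could as easily create a mismatch as prevent one. Because both concentrations are kept, the separate report can use whichever convention fits.
- **Review during the study.** With nothing tested and no threshold on PTR, there is no favourable result to select.
- **Cost.** Giving the 12 h sample its own parameter name would conflict with the endpoint lists in both documents, Protocol Table 1 and SAP Table 3. It would also raise the question whether a primary endpoint definition had changed, which under Protocol Section 9 calls for an amendment if the change is major.

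**Conclusion.** No change to the plan is needed. This is a small gap in a definition that analysts will fill sensibly: they will show the two Day 10 values under their own time labels and footnote the one used for PTR. Either denominator is a valid steady-state trough and gives a sound descriptive PTR, and no conclusion of the study turns on the choice.

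With 12 participants and assumed CVs of 10% to 30%, the geometric mean PTR under the two choices would typically agree within about 8% to 26%, centred on no difference. This rests on assumed CVs, independent errors and no systematic difference between the two troughs; the timing factors rest on assumed half-lives. None of these comes from the documents, so the figures only illustrate the size. The judgement itself needs only what the plan states: steady state well before Day 10, a descriptive analysis, and full listing of both concentrations with their times.
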